2. PROTOCOL SYNOPSIS

Protocol Title: A Phase I/IIa safety and efficacy study of a synthetic bioactive bone graft device for cranial bone regeneration in adults

Protocol Number:

Investigational Product: Plasmid DNA (pln.247-pBI, 200 µg/ml) for transient expression of human perlecan domain 1 with 100 µg/ml rhBMP-2 in a gelatin/ tricalcium phosphate scaffold for cranial bone regeneration (B-247 Cranial Bone Graft Implant).

Placebo (Vehicle): none

Sponsor: Agenta Biotechnologies, Inc.
[name]
[name]

Study Site: UAB Health System
Birmingham, Alabama

Investigator: [name].
Division of Neurological Surgery
[name]
[name]
[name]

Name of IRB: Western IRB
[name]
[name]

Proposed Start Date: Quarter 3, 2013

Study Duration: For each subject, from day of device implant to final clinic visit at 1 year, with follow-up through 2 years.

Study Objectives: The objectives of this study are as follows:

- To evaluate the safety of a B-247 Cranial Bone Graft Implant
- To evaluate bone regeneration associated with placement of the B-247 Cranial Bone Graft Implant.

Study Design: Single center, single dose study unblinded safety and efficacy trial.

Number of Subjects: 12 total subjects, one group

	Number of Subjects	Dose Level
Group 1	12	200 µg/ml pln.247-pBI + 100 µg/ml rhBMP-2

Study Population: Trauma and Surgical Craniotomy patients, male, 19 to 59 years of age

Route of Administration: Localized direct surgical placement of investigational product in cranial defect

Dose and Schedule: Subjects will receive investigational product at time of surgery.

General Study Conduct: Subjects who consent to participate in the trial will be screened for eligibility immediately. Baseline data, including pre-operative CT images, will be made prior to surgery. Subjects and investigators will be unblinded to the treatment.

- 1) in-hospital surveillance for the first 7 days after administration of investigational product;
- 2) in-clinic physical assessments on Days 0, 3, 7, 42, 180, and 360;
- 3) lab testing at Days 0, 7 and 42;
- 4) solicited adverse events (AEs) recorded on diary cards for 1 years after administration; and during phone contact at 2 yr. follow-up.
- 5) collection of unsolicited adverse events during active follow up to Day 360 and during phone contact at 2 year follow-up.

Subjects will receive compensation for their time and effort at the completion of each clinic visit beginning with the 6 week follow-up.

Data and Safety Monitoring: The first three subjects will be enrolled at a rate of no more than one subject per week. After review of the 7 day safety data for each of the first 3 subjects, the Safety Review Committee (SRC) will recommend either to open enrollment for the remaining subjects or to discontinue enrollment. The SRC will review the occurrence of AEs weekly, with 24 hour reporting for SAEs. Stopping rules will be defined in the protocol.

Monitored Parameters:

Safety:

- Hematology, blood chemistry, urinalysis
- Vital signs and physical assessments
- Unsolicited and solicited adverse events (clinic visits, diary cards and telephone contacts)
- Follow-up safety surveillance through 2 years

Bone Regeneration:

- CT analysis

Endpoints:

Safety:

- Incidence of local adverse events including ectopic bone formation if any
- Incidence of systemic adverse events
- Incidence of changes to laboratory parameters relative to baseline values

Bone Regeneration:

- The proportion of subjects at Day 42 and 180 and 360 with evidence of mineralized bone regeneration at the site of the original cranial defect relative to baseline (Day 0)
- The percentage of bone regeneration in the original cranial defect at Day 42 and 180 and 360 relative to 0% at baseline (Day 0)

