3. SCHEDULE OF EVALUATIONS

Visit Number	Screen	Visit 1	Contacts 1 and 2	Visit 2	Visit 3	Visit 4	Visit 5	Visit 6	Contact 3
Trial Timeline	Day -21 to 0	Day 0	Days 1 and 2 ¹	Day 3	Day 7	Day 42	Day 180 ¹	Day 360 ¹	Days 720 ¹
Visit/Contact Window (Days)	N/A	N/A	+/- 0	+/- 1	+/- 1	+/- 4	+/- 28	+/- 28	+/- 28
Informed Consent	X								
Inclusion/Exclusion	X	X							
Medical History	X								
Interim Medical History		X	X	X	X	X	X	X	X
Concomitant Medications	X	X	X	X	X	X	X	X	
Physical Examination	X								
HIV and Illicit Drug Test	X								
Physical Assessment: Vital Signs ² /Node Check		X		X	X	X	X	X	
Safety Labs (CBC, Blood Chemistry, PT, PTT, Urinalysis) ^{2,3}	X	X			X	X			
Surgical Treatment		X							
Surveillance (30 minutes)		X							
CT	X	X				X	X	X	
Diary Cards Distributed/Collected		X			X	X	X	X	X
Unsolicited Adverse Events		X	X	X	X	X	X	X	X

¹ Subjects will be contacted at Days 1 and 2, Days 42 and at 6 months, 1 year, and 2 years with a scripted telephone contact for safety follow-up and scheduling.

² Vital signs and laboratory values will be evaluated using the appropriate FDA draft guidance.

³ Any abnormal laboratory result arising post-administration, and of moderate or greater severity, will be followed until results return to baseline value or for the duration of safety follow-up.

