7. STUDY DESIGN

7.1 Study Overview

This is a single center, unblinded, safety and efficacy study.

A total of 12 subjects will be enrolled.

All 12 subjects will receive the B-247 Cranial Bone Graft Implant.

Enrollment will begin with 3 subjects enrolled at a rate of no more than one subject per week. The second, and third subjects will only be treated with the experimental device if stopping rules (see Section 14.3) are not met and other safety concerns are absent. Following review of Day 7 safety data for each of the first 3 subjects, the SRC will determine whether to open enrollment to the remaining 9 subjects or to discontinue enrollment. The SRC will review the occurrence of AEs weekly, with 24 hour reporting for SAEs. Stopping rules are described in full in Section 14.3.

Safety will be assessed in all participants. Each participant will be requested to record solicited AEs daily for 2 years after their device placement using study diary cards. Additionally, unsolicited adverse events will be collected immediately following surgical device placement through two years via telephone contacts and at clinic visits. Serious adverse events (SAEs) will be collected throughout the 2 year period of safety surveillance.

Safety evaluation will include hematologic and biochemical toxicity evaluation.

Blood and urine samples will be collected at screening (Day -21 to -1), on Day 0 prior to administration of the device, and again on Days 7, and 42 to measure the effects of device on blood chemistry, urinalysis, and hematology. The urine and blood samples obtained on Day 0 will be used for the baseline comparison.

Subjects will be asked to undergo a physical examination at screening (Day -21 to -1) and a physical assessment including vital signs, lymph node exam, and symptom directed exams at all clinic visits following enrollment (Days 0, 3, 7, 42, 180, and 1 year).

Telephone contacts will occur on the first two days after surgery (Days 1, 2) for study staff follow-up on possible adverse events. In addition, telephone contacts will be made after two years to document the occurrence of SAEs and the resolution of AEs ongoing at the one-year visit.

The overall safety assessment of the device will be based on the incidence of local and systemic reactogenicity, the incidence of changes to laboratory parameters relative to baseline values, and solicited and unsolicited adverse events.

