8.3 Prior and Concomitant Therapy

Notwithstanding above exclusions (section 8.2), standard medical protocol for pre-existing medications and post-operative management will apply, including post-operative instructions by the physician.

Participants will be advised that they are not to receive other investigational products (drug or vaccine) for 180 days post vaccination.

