9. STUDY PROCEDURES

Recruitment for this trial will begin following receipt of all regulatory and ethics committee approvals and will conclude when 12 subjects have completed the 6-week visit.

When the site pharmacist is notified that the subject is available for device placement, the unblinded pharmacist will withdraw a device package from the refrigerator. The principle investigator will prepare the experimental device by cutting or shaping to fit the subject's cranial defect. The experimental device will be wetted, then placed into the defect in the same manner as placing an autologous bone graft, taking care to fit the device to the margins of the defect in all dimensions. The experimental site may or may not be covered with a vicryl screen for tissue support, and the wound will be closed by conventional means.

The preliminary safety assessment will be available approximately four months after enrollment has been completed. Follow-up of subjects will continue through two years.

Source documents will include subject diary cards, subject medical charts, telephone contact records, reports from clinical laboratory tests, and analytical results from tests conducted on clinical samples by Agenta and its contractors. Results of in-clinic assessments, as well as AE and SAE information, will be recorded directly onto

protocol Case Report Forms (CRFs) or will be transferred from source documents onto CRFs. Results of tests on clinical samples will be transferred directly from the source documents into the study database.

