9.1 Study Visits

Screening Visit (Day -21 to -1)

Participants will be screened for eligibility to participate in the study. The following procedures must be performed during the screening period:

- a. Obtain Informed Consent prior to any study procedures.
- b. Check eligibility criteria.
- c. Obtain medical history.
- d. Record concomitant medication
- e. Perform physical examination.
- f. Obtain blood samples (10 mL + 5 mL) for screening clinical laboratory assessments.
- g. Obtain a blood sample (4 mL) for HIV serology and illicit drug screen.
- h. Obtain CT image of cranial defect.

Visit 1 (Day 0, Baseline)

- a. Confirm that the subject wishes to remain in the trial.
- i. Confirm eligibility criteria as needed.
- j. Obtain interim medical history as needed.
- k. Record concomitant medication as needed.
- l. Perform physical assessment as needed.
- m. Obtain blood samples (10 mL + 5 mL) and urine sample for clinical laboratory assessments if more than 3 days since prior screening.
- n. Obtain blood sample (4 mL) for PT and PTT tests if more than 3 days since prior screening.
- o. Administer experimental device.
- p. Keep the subject under observation for 30 minutes post administration and record any reaction in the source documents and CRF.
- q. Give participant the diary card with instructions for use.
- r. Record AEs and SAEs.
- s. Set up appointment for Visit 2 (Day 3).

Contact 1 (Day 1)

- a. Record symptoms and symptom severity on Telephone Contact Symptom Assessment Form.
- b. Record AEs and SAEs.
- c. Schedule in-clinic evaluation for moderate or severe AEs or SAEs, as clinically appropriate.

Contact 2 (Day 2)

- a. Record symptoms and symptom severity on Telephone Contact Symptom Assessment Form (Appendix D).
- b. Record AEs and SAEs.
- c. Schedule in-clinic evaluation for moderate or severe AEs or SAEs, as clinically appropriate.

Visit 2 (Day 3)

- a. Confirm that the subject wishes to remain in the trial.
- b. Obtain interim medical history.
- c. Review diary card with subject.
- d. Record concomitant medication.
- e. Perform physical assessment (vital signs, lymph node exam, and symptom directed exam).
- f. Record AEs and SAEs.
- g. Set up appointment for Visit 3 (Day 7).

Visit 3 (Day 7)

- a. Confirm that the subject wishes to remain in the trial.
- b. Obtain interim medical history.
- c. Record concomitant medication.

- d. Perform physical assessment (vital signs, lymph node exam, and symptom directed exam).

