- d. Verify telephone contact information and mailing address and provide instructions to participant in the event of a change in contact information.

Additional Clinic Visits

Any subject with an abnormal laboratory result or who experiences an adverse event may be requested to come into the clinic for additional follow-up evaluation not specified by the protocol if this is deemed medically prudent by the investigator.

9.2 *Obtaining, Handling, Storage, and Shipment of Specimens*

9.2.1 *Blood Samples for Safety Laboratory Tests*

Blood samples collected for safety analysis will be labeled and handled per the local reference laboratory standard operating procedures for hematology and biochemistry profiles. Blood samples for safety laboratory tests will include one 5 mL and one 10 mL sample, as well as one 4 mL sample for PT and PTT testing where specified.

9.2.2 *Urine Samples*

A clean-catch urine sample will be collected by each participant for safety evaluation. Study personnel will be responsible for instructing subjects on this technique. Urine samples will be handled and labeled per the local reference laboratory standard operating procedures for urinalysis.

9.3 *Safety Data Review*

The SRC will perform a review of the safety data through seven days post-administration for the first three subjects, and through seven days post-administration for all subsequent subjects. The SRC will use the following evaluation criteria to approve the completion of enrollment after the first 3 subjects:

- a) Absence of SAEs or severe AEs "definitely", "probably" or "possibly" related to the experimental device.
- b) No evidence of severe hematologic or biochemical toxicity.
- c) No consistent pattern of AEs that, in the judgment of the SRC, represents a significant threat to the safety of the subjects with continued enrollment.

Approval from Agenta will be obtained before proceeding with treatment of subjects 4-12.

9.4 *Compliance with Protocol*

All participants who receive the experimental device will be included in the safety evaluation.

The following events are to be considered sufficient reason for discontinuation of a participant from the study:

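### The synopsis puts the first 7 days in hospital, but the schedule and visit sections are written for a subject at home, and no section specifies a daily temperature in week 1

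*Protocol*

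**What the plan says.** **Synopsis (Section 2, General Study Conduct).** The first item is "in-hospital surveillance for the first 7 days after administration of investigational product". The second item, beside it, lists clinic assessments that include Days 3 and 7.

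**Schedule (Section 3).** Days 1 and 2 are scripted telephone contacts. Vital signs fall on Days 0, 3 and 7 within the first week. The windows are 0 days for the two calls and 1 day either side for the Day 3 and Day 7 visits. The only surveillance row is 30 minutes on Day 0.

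**Section 7.1.** "Telephone contacts will occur on the first two days after surgery (Days 1, 2) for study staff follow-up on possible adverse events". Day 3 is listed as a clinic visit.

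**Section 9.1.** Visit 1 ends with staff booking the Day 3 appointment. At each of the two calls staff are told: "Schedule in-clinic evaluation for moderate or severe AEs or SAEs, as clinically appropriate".

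**Section 11.1.2.** Participants watch for events, fever among them, every day for six weeks. Diary Card #1 covers local and systemic events up to Day 7. The digital thermometer is supplied on Day 7, for oral temperature in weeks 1-6.

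**Section 9.3.** "The SRC will perform a review of the safety data through seven days post-administration for the first three subjects". The committee's view on subjects 4-12 follows from that review.

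**The concern.** A site cannot follow both sets of instructions as written. Staff do not telephone a subject on their own ward, book him an appointment two days later, or schedule a clinic evaluation for an event he has there. A site working from the visit sections would not deliver the surveillance that the synopsis promises.

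The thermometer date follows from the same unresolved question. Day 7 makes sense as a discharge handout after a 7-day stay. For a subject already at home it comes a week late. For a subject in hospital, no section asks for ward temperatures to be recorded as study data. Under either setting, the daily watch for fever in week 1 has no daily measurement specified behind it.

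Week 1 matters because it decides whether treatment opens to the remaining nine subjects. Section 5.5 says that there is no earlier human experience with this plasmid approach.

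**Working it through.** The documents give no figure to reproduce, so the check compares the instructions and then counts days.

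**Do the instructions fit a 7-day inpatient stay?**

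| Instruction | Where | Fits? |
|---|---|---|
| 30 minutes' observation on Day 0 | Schedule, 9.1, 11.1.1 | Yes; 11.1.1 uses it as the window for immediate events |
| Telephone calls on Days 1 and 2 | Schedule, 7.1, 9.1 | No |
| Booked appointment for Day 3 | 9.1 | No |
| Clinic evaluation scheduled after a reported event | 9.1 | No |
| Thermometer on Day 7 | 11.1.2 | Yes, as a discharge handout |

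**Days without scheduled staff contact, Days 1-7, nominal dates.** Contacts fall on Days 1, 2, 3 and 7. Let D be the last day in hospital, which the visit sections do not give, so it is varied here.

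- D of 3 or less: Days 4, 5 and 6 uncovered, 3 per subject; 3 × 3 = 9 of 21 subject-days for the first three subjects.
- D = 4: Days 5 and 6; 2 × 3 = 6 of 21.
- D = 5: Day 6; 1 × 3 = 3 of 21.
- D of 6 or more: 0 of 21.

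**With the visit windows.** Visit 2 may fall on Day 2 and Visit 3 on Day 8. If the subject has left hospital by Day 2, Days 3-7 are uncovered: 5 per subject, 5 × 3 = 15 of 21. The nominal 9 is therefore not a maximum.

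**Days without scheduled vital signs, Days 1-7.**

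- Nominal dates: vital signs on Days 3 and 7, so 7 − 2 = 5 of 7 lack them; 5 × 3 = 15 of 21.
- Visit 2 on Day 2 and Visit 3 on Day 8: vital signs on Day 2 only, so 7 − 1 = 6 of 7; 6 × 3 = 18 of 21.

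Reading these as temperature counts assumes that vital signs include temperature, which the protocol does not say. If they do not, nominal Days 1-6 have no specified reading: 6 of 7, or 18 of 21. If ward charts hold daily temperatures through the week, the count is 0.

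**The case against.** The strongest reply is that the subjects probably are in hospital. They have had cranial surgery, and Section 8.3 says that "standard medical protocol for pre-existing medications and post-operative management will apply". The synopsis lists the hospital stay and the clinic assessments side by side, so its author evidently thought them compatible. Section 9 states: "Source documents will include subject diary cards, subject medical charts, telephone contact records". Ward temperatures could therefore reach the database. This stands as far as it goes: discharge before Day 7 is stated nowhere, and the loss may be nil. But the protocol does not require ward readings, and the telephone calls and clinic scheduling remain unexplained.

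On the thermometer, weeks 1-6 can be read as the interval from the end of week 1 (Day 7) to Day 42, which is the Diary Card #2 period. The daily instruction asks for watching for fever, not for a reading each day. That makes the sentence workable, but week 1 still has no daily measurement.

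The link to the committee's decision is also limited. Section 9.3 turns on related serious or severe events, severe laboratory toxicity and a worrying pattern of events. Section 11.1.4 grades events and abnormal vital signs mainly by their effect on activity, so a missing temperature would not by itself change a grade. Symptom forms on Days 1 and 2, Diary Card #1, visits on Days 3 and 7 and Day 7 laboratory tests remain in place. This holds, and it keeps the point minor.

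**Conclusion.** Wrong as written, at the low end of what should be changed. The first-week setting is contradictory, and that rests on the text alone. Any consequence for the data depends on the assumed discharge day, the actual visit dates, whether vital signs include temperature, and what ward charts hold. The range runs from zero to 5 days per subject without scheduled contact and 6 of 7 without vital signs. No sample size, probability or stopping rule changes.

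A reader might infer more, and the documents do not support it:

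- **That 30 minutes of observation contradicts 7 days.** It is a window for immediate events and can sit inside a hospital stay.
- **That subjects are sent home early.** This is an inference from the calls and appointments. The rule in Section 11.1.4 that a participant calls the site about a severe event runs through all follow-up and says little about week 1.
- **That the decision on subjects 4-12 is unsound.** Its criteria and most of its inputs are the same under either setting.
- **That the definition of a serious event needs rewording.** Section 10 already covers hospitalization and its prolongation.

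**What to change.** State one first-week setting in the synopsis, the schedule, Section 7.1 and Section 9.1.

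- **If the 7-day stay is kept:** replace the Day 1 and 2 calls and the Day 3 appointment with ward adverse event assessments and a recorded daily temperature through Day 7. The Day 7 thermometer handout can then stay.
- **If it is not kept:** delete the synopsis item and supply the thermometer on Day 0 or at discharge, with ward temperatures recorded until then.

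The cost is protocol wording plus either a daily ward reading on the case report form or a thermometer handed out up to 7 days sooner.

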5. INTRODUCTION

5.1 Investigational Product Description

[figure not shown]
The B-247 Cranial Bone Graft Implant is an experimental device which consists of plasmid DNA (pln.247-pBI, 200 $\mu\text{g}/\text{ml}$ of implant volume) for transient expression of human perlecan domain 1 with 100 $\mu\text{g}/\text{ml}$ rhBMP-2 in a gelatin/tricalcium phosphate scaffold for cranial bone regeneration. The product is provided as a pliable solid single-phase unit consisting of 80% bioactivated tricalcium phosphate (TCP) crystals 200-600 μm particle size, evenly distributed within a 20% cross-linked gelatin polymer. The implant is bioactivated by incorporating plasmid DNA lipoplexes and rhBMP-2 in 1% sucrose excipient, then lyophilizing the loaded implant to a final concentration of 200 $\mu\text{g}/\text{ml}$ of implant of pln.247-pBI plasmid and 100 $\mu\text{g}/\text{ml}$ of implant of rhBMP-2. Plasmid lipoplexes are derived from incubating pln.247-pBI plasmid with Lipofectamine 2000 in a 2:1 ratio for 30 minutes. Sucrose, plasmid, rhBMP-2, Lipofectamine 2000, TCP crystals, and gelatin are each manufactured separately according to cGMP and combined under sterile conditions in a clean room.

- rhBMP-2 is marketed in the US as a component of the InFuse™ device kit by Medtronic, Inc. This kit was approved under PMA P050053 on 03/13/2007. The rhBMP-2 is manufactured in a human CHO cell line.
- Tricalcium phosphate crystals are marketed in the US as Osteogen by Implants. This product was approved under 510(k) Premarket Notification on 5/31/1995.
- Sucrose and gelatin are common excipients and are purchased cGMP quality.
- Lipofectamine 2000 is purchased from Life Technologies as a cGMP grade cationic lipid.
- The pln.247-pBI expression plasmid is manufactured by Aldevron in a cGMP manner derived from *E. coli* fermentation.

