5.5 Rationale for Phase I Study of B-247 Cranial Bone Graft Implant

Agenta has performed a series of *in vitro* experiments clearly demonstrating the ability of the recombinant that is expressed by pln.247-pBI plasmid (rPln.247) to augment growth factor activities.

In vivo Safety Data: doses of pln.247 from 40 µg/ml to 360 µg/ml graft volume have shown no signs of toxicity, or general morbidity. While TCP stimulated BMP-2 associated intramembranous bone formation that was juxta-proximal to the particles, (see (2)), and new bone that was contiguous with the maxilla, remnants of TCP particles remain embedded within the new bone for at least 12 weeks. The histopathology on >200 maxillary bone defects treated with doses ranging from 40 µg/ml to 360 µg/ml graft volume show no local pathology or acute bone resorption attributable to biologics. The CBC and clinical chemistry safety data showed hematology and clinical chemistry values within normal limits for aging rats.

Conclusion

- pln.247 plasmid more than doubles the dose-effectiveness of BMP-2 osteogenic activity for *in vivo de novo* bone generation
- B-247 formula of TCP, BMP-2, and pln.247 plasmid is superior to OsteoGen TCP bone graft
- B-247 provides more than 5 times as much maxillary ridge augmentation than InFuse™ using ≈1/50th of the BMP-2 dose
- B-247 formula generated new bone with 4 fold greater density than new bone generated by InFuse™.
- B-247 did not cause osteonecrosis in the first 3 weeks post-implant as did InFuse™.

There is no previous human experience with plasmid DNA augmentation of the perlecan domain 1. There is a large body of data regarding the use of 1.5 mg/ml rhBMP-2 in craniofacial and orthopedic bone regeneration (InFuse®) and for rhBMP-7 (OP-1®). The data suggest that the dose of rhBMP required for the partial clinical efficacy is almost too great and poses a poor risk/benefit ratio. Therefore, the trial of an experimental product such as B-247 Cranial Bone Graft Implant, which has the potential to significantly lower the dose of rhBMP-2 while improving the efficacy with the safe addition of a relatively low level of plasmid DNA would be of great value to the field of medicine.

Subsequent clinical studies will evaluate the safety and efficacy of the B-247 Cranial Bone Graft Implant in direct comparison to other clinically accepted methods for treatment.

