Information will be collected on the osteoinduction associated with the device. A CT scan will be performed on each subject at baseline prior to placement of the device, then again at day 42, day 180, and at one year.

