13.2 Variables and Timepoints of Measurement

13.2.1 Safety Variables

In-clinic safety evaluation on Days 0, 3, 7, 42, 180, and 360 will be graded for severity and relationship to the study agents and will include:

- a) Rates of SAEs and their relationship to device placement, through 2 years of long-term follow-up.
- b) Rates of local or systemic solicited AEs and their categories (mild, moderate and severe), through Day 360 ± 28 days.
- c) Rates of reported unsolicited AEs, through Day 360 ± 28 days.
- d) Hematologic and biochemical toxicity evaluation following device placement.

Osteogenicity will be evaluated using radiographs and CT scans obtained from participants on Day 0 (baseline, pre-implantation), Day 42 (± 7), 6 weeks after device placement), and Day 180 (± 14) 6 months after device placement).

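### Both CT bone endpoints are referenced to a pre-implant scan of a defect that is then filled with an 80% tricalcium phosphate graft, so residual scaffold can be read as regenerated bone, most clearly at Day 42

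*Protocol*

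**What the plan says.** **Endpoints.** The Protocol Synopsis lists two bone endpoints at Days 42, 180 and 360. One is a percentage: "The percentage of bone regeneration in the original cranial defect at Day 42 and 180 and 360 relative to 0% at baseline (Day 0". The other is the proportion of subjects with "evidence of mineralized bone regeneration at the site of the original cranial defect relative to baseline (Day 0". Only the percentage endpoint has its baseline fixed at 0%; the proportion endpoint names Day 0 as reference without giving a value.

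**Timing of the reference scan.** Section 7.1 puts the CT "at baseline prior to placement of the device, then again at day 42, day 180, and at one year". Section 13.2 says the images are "obtained from participants on Day 0 (baseline, pre-implantation". The Schedule of Evaluations marks a CT at Screening and another at Visit 1, without saying whether the Visit 1 scan comes before or after surgery. The Visit 1 procedure list in Section 9.1 contains no CT.

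**What fills the defect.** Section 5.1 describes a "pliable solid single-phase unit consisting of 80% bioactivated tricalcium phosphate (TCP) crystals" in cross-linked gelatin. Section 12.2 has enough graft applied to fill the defect, and Section 9 has the surgeon place it "taking care to fit the device to the margins of the defect in all dimensions".

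**Persistence.** Section 5.5 reports from the sponsor's animal work that "remnants of TCP particles remain embedded within the new bone for at least 12 weeks".

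**Assessment.** Section 11.2.1 names CT analysis as the method. Section 13.3.2 says only that osteoinduction will be evaluated. Section 7.1 gives the implant to all 12 subjects, so there is no scaffold-only comparison.

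**The concern.** The reference scan shows the defect without graft. Every later scan shows it after a graft made mostly of calcium phosphate has been placed. Section 5.2 describes bone itself as 70% inorganic calcium phosphate by weight, so graft and target tissue share a mineral class. The difference between a pre-implant scan and a later one therefore contains two components: new bone and whatever scaffold mineral remains. The planned scans cannot separate them by subtraction, because none records the mineral present just after placement.

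At stake is the interpretation of the secondary objective. A rise from baseline could reflect osteoinduction, retained TCP, or both. The missing scan cannot be recovered once a subject has been implanted, and no later analysis plan can supply it.

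**Working it through.** The plan gives no hypothesis, threshold, power or variance for the CT endpoints, and the 0% is a definition, so there is no plan figure to reproduce. The check is of timing and of what the definition credits.

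**1. Timing against the protocol's own persistence figure**
- TCP remnants: at least 12 weeks = 12 × 7 = 84 days (Section 5.5, animals).
- Day 42 scan at its latest: 42 + 4 = Day 46 under the Schedule of Evaluations, or 42 + 7 = Day 49 under Section 13.2. Both are well short of 84, so some TCP is to be expected at this visit if the animal data carry over.
- Day 180 scan at its earliest: 180 − 28 = Day 152. The 12-week figure is a lower bound and does not reach this far. The protocol gives no human resorption figure, so it does not settle what remains at Days 180 and 360.

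**2. What the percentage endpoint returns if mineral is read as bone**

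Let f be the share of defect volume that CT reads as mineral just after placement, r the share of that mineral remaining at a later scan, and b the share of the defect filled by true new bone. Treat b and residual scaffold as additive. None of these values is in the protocol. The 80% TCP content has no stated weight or volume basis, and Section 5.3 calls the scaffold porous, so f is varied from 0.2 to 0.8.

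- Pre-implant reference: apparent regeneration = b + f × r
- Post-placement reference: apparent change = b + f × (r − 1)

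With no new bone (b = 0):

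| f | r | Pre-implant reference, f × r | Post-placement reference, f × (r − 1) |
|---|---|---|---|
| 0.8 | 1 | 80% | 0% |
| 0.8 | 0.5 | 40% | −40% |
| 0.8 | 0.25 | 20% | −60% |
| 0.8 | 0.1 | 8% | −72% |
| 0.2 | 1 | 20% | 0% |
| 0.2 | 0.5 | 10% | −10% |
| 0.2 | 0.25 | 5% | −15% |
| 0.2 | 0.1 | 2% | −18% |

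Against the pre-implant scan the result is positive whenever any detectable TCP remains and is read as bone. It is zero only if r = 0.

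**3. Why simple subtraction does not solve it**

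The last column shows the opposite error. True bone is cancelled when b = f × (1 − r). At f = 0.8 and r = 0.5 that is 0.8 × 0.5 = 0.40, so new bone filling 40% of the defect would be reported as no change. A post-placement scan is needed, but so is a criterion for telling bone from TCP.

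**4. Whether the plan contains a safeguard**

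Three would serve: a post-placement reference scan, a scaffold-only group, or a stated CT criterion. The text describing the baseline scan excludes the first, the single-arm design excludes the second, and the third is not stated.

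**The case against.** The strongest reply is that the endpoints are worded as bone regeneration, not as mineral in the defect. Regenerated bone on Day 0 is truly 0% whichever scan is used, so the baseline definition is not itself an error. Scaffold is credited only if the reading fails to separate TCP from bone, and a shared mineral class does not prove the same appearance on CT. Reading rules often sit in an analysis plan or imaging manual that is not shown. This stands in part: the absence of a reading rule from the protocol is not by itself the defect. Scan timing, however, is fixed in the protocol.

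Several stronger conclusions are tempting and are not supported:

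- **All 12 subjects would be false responders at Day 42.** That is an assumed worst case requiring every reader to score residual TCP as bone. The Section 5.5 sentence describes remnants inside new bone in animal maxillary defects, not a graft with no osteoinduction.
- **The secondary objective cannot be answered.** Nothing in the protocol shows how much TCP remains at Days 180 and 360; the bias there could be nil.
- **The defect volume cannot be measured because the defect is made at the study operation.** The Synopsis admits surgical craniotomy patients and the exclusion criteria bar previous cranial surgery, which points that way. Section 6.2 speaks of existing defects, and Section 9.1 has the Screening CT image the defect. The text is ambiguous.
- **The trial fails because it cannot separate the device from inert filler.** Section 5.5 leaves direct comparison with other treatments to later studies.

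It is also fair that the primary objective is safety, and that the enrolment and stopping decisions in Sections 9.3 and 14.3 use safety data only.

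**Conclusion.** The concern holds in a limited form. Both CT endpoints are referenced to a scan taken before a largely calcium phosphate graft fills the defect. With no post-placement scan before Day 42, no scaffold control and no stated bone-versus-TCP criterion, residual scaffold can be read as regenerated bone. The protocol's own persistence figure makes this expected to be possible at Day 42. At Days 180 and 360 the direction is the same if TCP remains, but the size is unknown.

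The 2% to 80% range illustrates sensitivity; it does not estimate the bias. It rests on assumed f and r, and on a reading that counts mineral as bone. The effect is confined to interpretation of the secondary efficacy result. The correction is inexpensive and has to be made before the first implant, because the reference image cannot be obtained afterwards.

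**What to change.** 1. Keep the Screening CT as the pre-operative scan. Specify that the Visit 1 CT already marked in the Schedule of Evaluations is taken after placement, as the reference for graft and defect volume and for initial scaffold mineral.
2. Report both endpoints against the pre-operative and the post-placement scans, using a CT criterion for new bone versus residual TCP that is fixed before any scan is read. Mineralization continuous with the defect margin is one example. Because the graft is itself shaped to meet that margin, continuity should be judged against the post-placement scan. Do not rely on plain subtraction.
3. Label the Day 42 bone result descriptive and confounded by scaffold.
4. Reconcile the Synopsis endpoints, the Schedule of Evaluations, Section 7.1, the Visit 1 list in Section 9.1 and Section 13.2 on whether and when a Day 0 CT is done.

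**Cost.** Against the Schedule of Evaluations the number of scans is unchanged. If Sections 7.1 and 9.1, which describe a single baseline CT, reflect actual practice, it is one more scan per subject, or 12 in all. The second pre-operative scan is lost, and the Day 42 figure is likely to look less favourable. The criterion needs some imaging work before enrolment.
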